3.2 Post Study Access to Therapy

At the conclusion of the study, subjects who continue to demonstrate clinical benefit will be eligible to receive study drug. Study drug will be provided via an extension of the study, a rollover study requiring approval by responsible health authority and ethics committee or through another mechanism at the discretion of the sponsor. The sponsor reserves the right to terminate access to study drug if any of the following occur: a) the marketing application is rejected by responsible health authority; b) the study is terminated due to safety concerns; c) the subject can obtain medication from a government sponsored or private health program; or d) therapeutic alternatives become available in the local market.

3.2.1 Withdrawal of Consent

Subjects should be encouraged to continue participation in the trial until the laboratory definition of disease progression is met (Section 5.4.5.5). Subjects who discontinue study therapy before progression (eg, due to toxicity) should be encouraged to allow the necessary laboratory results (eg, M-protein data, radiologic data, calcium results) to be collected until progression criteria are fulfilled, even if the subject is on subsequent therapy (as per the PFS ITT definition in Section 8.3.1). These data can be obtained by the subject's local health care provider or the site staff and then analyzed and entered into the CRF/database by the central or local lab. Withdrawal of consent should be minimized because:

1. The subject in this trial who discontinues study therapy before progression will most likely subsequently be followed in any case by a healthcare provider locally or at the site via routine standard of care assessments (ie, monthly M-protein data, calcium, etc) and
2. In most cases, this protocol would not require any additional samples beyond those considered standard of care

If there is uncertainty about the progression criteria, investigators are encouraged to contact the BMS medical monitor/study director prior to:

1. starting a subject on another myeloma regimen or
2. performing the end of treatment visit for progression

Subjects who request to discontinue study drug will remain in the study and must continue protocol specified follow-up procedures. The only exception to this is when a subject specifically withdraws consent for any further contact with him/her or persons previously authorized by subject to provide this information. Subjects should notify the investigator of the decision to withdraw consent from future follow-up **in writing**, whenever possible. The withdrawal of consent should be explained in detail in the medical records by the investigator (and entered onto the appropriate CRF page), as to whether the withdrawal is from further:

1. study medication but subject is willing to continue to perform visits for PFS follow-up. study medication and study visits for PFS but agrees to provide the results of future myeloma assessments from another site/local site
2. study treatments, results from another site/local sites, but agrees to be contacted for overall survival follow-up

In the event that vital status (whether the subject is alive or dead) is being measured, publicly available information should be used to determine vital status only as appropriately directed in accordance with local law.

3.2.2 Lost to Follow-Up

All reasonable efforts must be made to locate subjects to determine and report their ongoing status. This includes follow-up with persons authorized by the subject as noted above. Lost to

follow-up is defined by the inability to reach the subject after a minimum of three documented phone calls, faxes, or emails as well as lack of response by subject to one registered mail letter. All attempts should be documented in the subject's medical records. If it is determined that the subject has died, the site will use permissible local methods to obtain the date and cause of death.

If investigator's use of third-party representative to assist in the follow-up portion of the study has been included in the subject's informed consent, then the investigator may use a Sponsor-retained third-party representative to assist site staff with obtaining subject's contact information or other public vital status data necessary to complete the follow-up portion of the study. The site staff and representative will consult publicly available sources, such as public health registries, obituary listings, and databases, in order to obtain updated contact information. If after all attempts, the subject remains lost to follow-up, then the last known alive date as determined by the investigator should be reported and documented in the subject's medical records.

3.3 Study Population

For entry into the study, the following criteria **MUST** be met.

3.3.1 Inclusion Criteria

1. Signed Written Informed Consent

- a) Subject is, in the investigator's opinion, willing and able to comply with the protocol requirements.
- b) Subject has given voluntary written informed consent before performance of any study-related procedure not part of normal medical care, with the understanding that consent may be withdrawn by the subject at any time without prejudice to their future medical care.

2. Target Population

- a) Age \geq 18 years or legal age of consent per local regulations.
- b) ECOG performance status \leq 2.
- c) Life-expectancy $>$ 3 months.
- d) Newly diagnosed, untreated, symptomatic, documented myeloma AND;
 - i) Who are not candidates for high-dose therapy plus SCT because of age (\geq 65 years) or coexisting conditions. Refusal to undergo high dose therapy with SCT is **NOT** sufficient for entry onto CA204006 for a subject $<$ 65 years old. There must be a comorbidity that prevents SCT for a subject $<$ 65 years old, AND;
 - ii) Measureable disease (patient must meet one of these criteria)
 - (a) serum IgG M-protein \geq 0.5 g/dL OR
 - (b) serum IgA M-protein \geq 0.5 g/dL OR
 - (c) serum IgM M-protein \geq 0.5 g/dL OR
 - (d) serum IgD M-protein \geq 0.05 g/dL OR
 - (e) Urine M-protein \geq 200 mg/24-hour

3. Age and Reproductive Status

- a) Women of childbearing potential (WOCBP) and men must be using 2 acceptable methods of contraception to avoid pregnancy throughout the study for a period of at least 1 month (4 weeks) before and women for up to 120 days, men for up to 180 days after the last dose of investigational product in such a manner that the risk of pregnancy is minimized. See [Section 3.3.3](#) for the definition of WOCBP and also refer to the Revlimid risk management plan guidelines.
- b) WOCBP must have a negative serum or urine pregnancy test (minimum sensitivity 25 IU/L or equivalent units of HCG). The first should be performed within 10 - 14 days and the second within 24 hours prior to the start of the investigational product. A prescription for lenalidomide for a female of childbearing potential must not be issued by the prescriber until negative pregnancy tests have been verified by the prescriber.
- c) Women must not be breastfeeding.
- d) Women who are not of childbearing potential (ie, who are postmenopausal or surgically sterile; see Section 3.3.3 for the definition of WOCBP) and men.
- e) Sexually active fertile men must use effective birth control if their partners are WOCBP. Men must agree to use a latex condom and a second form of birth control during sexual contact with WOCBP, even if they have had a successful vasectomy, and must agree to not donate semen during study drug therapy and for 180 days after therapy.
- f) Subjects must be willing to refrain from blood donations during study drug therapy and for 90 days after therapy.

3.3.2 Exclusion Criteria

1) Target Disease Exceptions

- a) Subjects with non-secretory or oligo-secretory or serum free light-chain only myeloma.
- b) Smoldering MM, defined as asymptomatic MM with absence of lytic bone lesions.
- c) Monoclonal Gammopathy of Undetermined Significance (MGUS) defined by all of the following: serum M protein < 3 g/dL, absence of lytic bone lesions, anemia, hypercalcemia and renal insufficiency related to monoclonal protein and (if determined) proportion of plasma cells in the bone marrow of 10% or less.
- d) Diagnosis of Waldenstrom's disease or other conditions in which IgM M protein is present in the absence of a clonal plasma cell infiltration with lytic bone lesions.
- e) Plasma cell leukemia (defined as either 20% of peripheral WBC comprised of plasma/CD138+ cells or an absolute count of $2 \times 10^9/L$).

2) Medical History and Concurrent Diseases

- a) POEMS syndrome (plasma cell dyscrasia with polyneuropathy, organomegaly, endocrinopathy, monoclonal protein, and skin changes).
- b) Significant cardiac disease as determined by the investigator including:
 - i) Known or suspected cardiac amyloidosis;
 - ii) Congestive heart failure of Class III or IV of the NYHA classification;
 - iii) Uncontrolled angina, hypertension or arrhythmia;

- iv) Myocardial infarction in past 6 months;
- v) Any uncontrolled or severe cardiovascular disease.
- c) Prior cerebrovascular event with persistent neurologic deficit.
- d) Known HIV infection or active hepatitis A, B, or C.
- e) Any medical conditions that, in the investigator's opinion, would impose excessive risk to the subject. Examples of such conditions include:
 - i) Any uncontrolled disease, such as pulmonary disease, infection, seizure disorder;
 - ii) Active infection that requires parenteral anti-infective treatment;
 - iii) Any altered mental status or any psychiatric condition that would interfere with the understanding of the informed consent.
- f) Prior or concurrent malignancy, except for the following:
 - i) Adequately treated basal cell or squamous cell skin cancer;
 - ii) Or any other cancer from which the subject has been disease-free for > 5 years.
- g) Uncontrolled diabetes (defined as Hgb A1C \geq 8.0%).
- h) Unable to tolerate thromboembolic prophylaxis including, aspirin, Coumadin (warfarin) or low-molecular weight heparin as clinically indicated.

3) Physical and Laboratory Test Findings

- a) Corrected serum calcium \geq 11.5 mg/dl within 2 weeks of randomization (despite appropriate measure such a short course of steroids, bisphosphonates, hydration, calcitonin).
- b) Absolute neutrophil count $<$ 1000 cells/mm³. No granulocyte colony stimulating factors (G-CSF or GM-CSF) allowed within 1 week of randomization. No pegylated granulocyte colony stimulating factors allowed within 3 weeks of randomization.
- c) Platelets $<$ 75,000 cell/mm³ ($75 \times 10^9/L$). Qualifying laboratory value must occur at most recent measurement prior to randomization and must be no more than 14 days prior to randomization. No transfusions are allowed within 72 hours prior to qualifying laboratory value.
- d) Hemoglobin $<$ 8 g/dL. Qualifying laboratory value must occur at most recent measurement prior to randomization and must be no more than 14 days prior to randomization. No transfusions are allowed within 72 hours prior to qualifying laboratory value.
- e) Total bilirubin \geq 2 x ULN or direct bilirubin \geq 2.0 mg/dL.
- f) AST or ALT \geq 3 x ULN.
- g) Creatinine clearance (CrCl) $<$ 30 mL/min measured by 24-hour urine collection or estimated by the Cockcroft and Gault formula:

$$\text{Female CrCl} = \frac{(140 - \text{age in years}) \times \text{weight in kg} \times 0.85}{72 \times \text{serum creatinine in mg/dl}}$$

$$\text{Male CrCl} = \frac{(140 - \text{age in years}) \times \text{weight in kg} \times 1.00}{72 \times \text{serum creatinine in mg/dl}}$$

4) Prior Therapy or Surgery

- a) Administration of systemic chemotherapy, biological, immunotherapy, clarithromycin or any investigational agent (therapeutic or diagnostic) for multiple myeloma except bisphosphonate therapy within 3 weeks prior to randomization.
- b) Treatment with plasmapheresis within 4 weeks prior to randomization.
- c) Steroids within 3 weeks of randomization, except:
 - i) short course (of ≤ 4 days) of 40 mg dexamethasone or equivalent for emergency use (baseline M proteins must be drawn after this short course and prior to randomization);
 - ii) ≤ 10 mg prednisone or equivalent per day;
 - iii) Steroid with little to no systemic absorption (ie, topical or inhaled steroids).
- d) Major surgery within 4 weeks prior to randomization (kyphoplasty is not considered major surgery); subjects should have been fully recovered from any surgical related toxicities.

5) Allergies and Adverse Drug Reaction

- a) Known hypersensitivity to lenalidomide, dexamethasone, any excipients in the elotuzumab formulation or recombinant protein.

6) Sex and Reproductive Status

- a) Sexually active fertile men not using 2 forms of effective birth control if their partners are WOCBP.

7) Other Exclusion Criteria

- a) Prisoners or subjects who are involuntarily incarcerated.
- b) Subjects who are compulsorily detained for treatment of either a psychiatric or physical (eg, infectious disease) illness.

Eligibility criteria for this study have been carefully considered to ensure the safety of the study subjects and to ensure that the results of the study can be used. It is imperative that subjects fully meet all eligibility criteria.

3.3.3 *Women of Childbearing Potential*

Women of childbearing potential include any female who has experienced menarche and who has not undergone successful surgical sterilization (hysterectomy, bilateral tubal ligation, or bilateral oophorectomy) or is not postmenopausal. Post menopause is defined as:

- Amenorrhea ≥ 24 consecutive months without another cause and a documented serum follicle stimulating hormone (FSH) level > 35 mIU/mL or
- Women with irregular menstrual periods and a documented serum follicle stimulating hormone (FSH) level > 35 mIU/mL or

NOTE: FSH level testing is not required for women ≥ 62 years old with amenorrhea of ≥ 1 year

- Women on hormone replacement therapy (HRT)

Women who are using oral contraceptives, other hormonal contraceptives (vaginal products, skin patches, or implanted or injectable products), or mechanical products such as an intrauterine device or barrier methods (diaphragm, condoms, spermicides) to prevent pregnancy, or are practicing abstinence or where their partner is sterile (eg, vasectomy) should be considered to be of childbearing potential.

[REDACTED]

[REDACTED]

[REDACTED]

[REDACTED]

[REDACTED]

[REDACTED]

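### Section 3.3.3 can class a woman with irregular periods and one raised FSH, or any woman on HRT, as postmenopausal, so the WOCBP-only contraception and pregnancy-test rules may not apply to her

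*Protocol*

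**What the plan says.** Section 3.3.3 of the Protocol defines post menopause by three bullets joined by *or*:

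- Amenorrhea of at least "24 consecutive months without another cause and a documented serum follicle stimulating hormone (FSH) level" above 35 mIU/mL.
- "Women with irregular menstrual periods and a documented serum follicle stimulating hormone (FSH) level" above 35 mIU/mL.
- "Women on hormone replacement therapy (HRT", with nothing added.

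A NOTE printed between the second and third bullets says "FSH level testing is not required for women" aged 62 or over who have had amenorrhea for at least a year. A closing paragraph returns some women to WOCBP status: users of hormonal or mechanical contraception, and those "practicing abstinence or where their partner is sterile (eg, vasectomy) should be considered to be of childbearing potential". It mentions neither irregular periods nor HRT.

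Section 3.3.1 uses this definition. Criterion 3.a says "Women of childbearing potential (WOCBP) and men must be using 2 acceptable methods of contraception", for women until up to 120 days after the last dose; it refers to Section 3.3.3 and also to the Revlimid risk management guidelines. Criterion 3.b requires negative pregnancy tests in WOCBP and adds: "A prescription for lenalidomide for a female of childbearing potential must not be issued by the prescriber until negative pregnancy tests have been verified". Criterion 3.d admits "Women who are not of childbearing potential (ie, who are postmenopausal or surgically sterile", again by reference to Section 3.3.3. The pregnancy-test rows of Tables 5.1-1, 5.1-2 and 5.1-3 are marked as WOCBP only.

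**The concern.** The second bullet undercuts the first. The same FSH value that needs two years of amenorrhea in one route is enough in the other for a woman who still has periods. One documented value suffices, with no minimum age and no repeat. The third bullet asks for no evidence of menopause at all.

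Both arms receive lenalidomide, which Section 4.1.3.2 describes as an analogue of a known human teratogen. A woman wrongly classed as postmenopausal could take it without the contraception, testing and prescription rules that the protocol attaches to WOCBP status. The event would be rare, but the harm severe and irreversible.

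**Working it through.** No power, alpha or event calculation bears on this. The check is to follow the classification from the definition to the rules that use it, and then to see what else in the protocol might protect the same woman.

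**Step 1: the classification.** Irregular periods plus one FSH above 35 meets bullet 2, so she is postmenopausal. HRT alone meets bullet 3, with the same result. No redaction mark falls inside the list.

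**Step 2: the effect.** Criterion 3.d admits her as not of childbearing potential. Criteria 3.a and 3.b and the three pregnancy-test rows are written for WOCBP and so may not reach her.

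**Step 3: the closing paragraph of Section 3.3.3.** If it overrides the bullets, contraceptive users, abstinent women and women with a sterile partner become WOCBP again. The women left outside are then those with none of these protections.

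**Step 4: safeguards that do not run through Section 3.3.3.**

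| Place | What it provides | What remains open |
|---|---|---|
| Criterion 3.a; Section 4.1.3.2; dispensing rows of Tables 5.1-2 and 5.1-3 | Lenalidomide only under the Revlimid Risk Management Plan, with contraception instruction and scheduled tests for those with pregnancy potential under the plan | The plan's classification of women is not in the documents |
| Section 4.1.3.2 | Advice to females in general to avoid pregnancy on lenalidomide and for up to 8 weeks afterwards | Shorter than criterion 3.a |
| Section 5.3 | Negative urine test before dosing in females with reproductive potential | The term is not defined in the available text, and a site could read it through Section 3.3.3 |

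**Step 5: the period after the last dose.** Section 6.4 builds the protocol's period for women as 90 days of washout + 30 days for one ovulatory cycle = 120 days, the figure in criterion 3.a. The advice in Section 4.1.3.2 is 8 × 7 = 56 days after lenalidomide. If the last doses of all study drugs fall on the same day, a woman covered only by that advice could lack up to 120 − 56 = 64 days of the protocol's period.

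**Step 6: tests missed.** Per affected woman, the range runs from none (the plan or Section 5.3 captures her) to the whole WOCBP schedule (neither does). The documents do not allow this to be narrowed.

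**The case against.** The strongest reply is that the protocol does not rest on Section 3.3.3 alone. Criterion 3.a itself points to the Revlimid plan, Section 4.1.3.2 makes the plan's conditions binding for every subject who is dispensed lenalidomide, and the Section 5.3 test is not written in WOCBP terms. This stands. A reader might infer that these women are left with no contraception or testing rule at all; the documents do not support that. What can be said is that the rules written through Section 3.3.3 may not apply, and that the other safeguards may or may not fill the gap.

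Two more tempting readings also fail. One is that the literal text of Section 3.3.3 removes these women from WOCBP status. Its lead sentence joins absence of sterilization and absence of menopause with *or*, so taken literally any unsterilized woman past menarche remains WOCBP. The classification set out here depends on the intent shown by criterion 3.d, which treats postmenopausal women as a separate group not of childbearing potential. The other is that Table 5.1-3, which asks for two-weekly tests in patients with irregular cycles, contradicts Section 3.3.3. It does not: a woman with irregular periods and FSH of 35 or below, or with no documented FSH, remains WOCBP, and the line applies to her.

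It is also fair to say that the documents do not establish how fertile a woman with irregular periods and FSH above 35 is. That she may still be fertile is a clinical assumption, though the first bullet, by requiring long amenorrhea on top of the same FSH value, does not treat that value as enough.

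**Conclusion.** The point holds as a weakness in a definition, and it is minor. Section 3.3.3, read as criterion 3.d intends, allows two groups to be classed as postmenopausal on evidence that does not establish menopause, and several lenalidomide safeguards follow that classification.

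The number affected is probably small, because entry below age 65 requires a comorbidity that prevents transplantation; the documents give no count. No endpoint, sample size or efficacy analysis changes. Confidence in the wording problem is good. Confidence in its practical consequence is limited, because that depends on how the Revlimid plan classifies these women and how sites read Section 5.3.

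**What to change.** In Section 3.3.3:

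1. Delete the irregular-periods bullet.
2. Replace the HRT bullet with: Women on HRT are WOCBP unless surgically sterile or they meet the amenorrhea and FSH criterion, which may be documented from before HRT started.
3. Place the existing NOTE under the amenorrhea bullet with its wording unchanged. Rewriting it so that one year of amenorrhea is sufficient in itself at age 62 or over could loosen the rule.
4. Add that where Section 3.3.3 and the Revlimid Risk Management Plan differ, the stricter classification applies. This avoids a new mismatch with a plan whose definition the protocol does not reproduce.

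The drafting cost is small. The burden falls on some truly postmenopausal HRT users who have no record from before HRT, mainly those under 62, and on women with irregular periods and FSH above 35. Both groups would need two-method contraception and the WOCBP pregnancy tests.

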3.5 Discontinuation of Subjects from Treatment

Subjects **MUST** discontinue investigational product (elotuzumab, lenalidomide, and dexamethasone) for any of the following reasons:

- Withdrawal of informed consent (subject’s decision to withdraw for any reason).
- Any clinical adverse event (AE), laboratory abnormality or intercurrent illness which, in the opinion of the investigator, indicates that continued participation in the study is not in the best interest of the subject.
- Pregnancy (Subject must discontinue elotuzumab and lenalidomide).
- Termination of the study by Bristol-Myers Squibb (BMS).
- Loss of ability to freely provide consent through imprisonment or involuntarily incarceration for treatment of either a psychiatric or physical (eg, infectious disease) illness.
- Progressive Disease (see [Section 5.4.5.5](#) for definition of disease progression).

- Subjects who receive any non-protocol specified systemic anti-myeloma therapy prior to documented progression will be discontinued from all study treatment (including lenalidomide/dexamethasone), however, tumor assessments must continue at 4 week intervals until documented progression.
- Subjects experiencing a Grade 4 infusion reaction must discontinue elotuzumab. Subjects may continue lenalidomide and dexamethasone treatment. Refer to [Section 4.3.2.2](#).
- Subjects experiencing angioedema, Grade 4 rash, exfoliative or bullous rash, Stevens-Johnson syndrome, or toxic epidermal necrolysis related to lenalidomide must discontinue lenalidomide. Subjects in the elotuzumab arm may continue elotuzumab and dexamethasone.
- Subjects experiencing a 28 day delay in all study drugs lenalidomide, dexamethasone, and elotuzumab due to an adverse event(s) related to study treatment must be discontinued from study drug. Subjects experiencing delays unrelated to study therapy, for example due to radiation therapy may delay study treatment up to 42 days. Delays greater than 28 days must be discussed with the medical monitor.

All subjects who discontinue should comply with protocol specified follow-up procedures as outlined in [Section 5](#). The only exception to this requirement is when a subject withdraws consent for all study procedures or loses the ability to consent freely (ie, is imprisoned or involuntarily incarcerated for the treatment of either a psychiatric or physical illness).

If a subject was withdrawn before completing the study, the reason for withdrawal must be entered on the appropriate case report form (CRF) page.

